B. Study Type and Design: Type of Study: multi-center prospective randomized controlled trial. Study Design: We will initially monitor 4 groups of patients. The first group (20 patients) will undergo bony tumor resection of the femur or proximal tibia and endoprosthetic reconstruction with TXA. The second group (20 patients) will undergo bony tumor resection of the femur or proximal tibia and endoprosthetic reconstruction without TXA. The third group (50 patients) will undergo soft tissue sarcoma resection of the lower extremity with TXA. The fourth group (50 patients) will undergo soft tissue sarcoma resection of the lower extremity without TXA. The use of TXA is well established for arthroplasty at this institution given the body of evidence supporting both efficacy and safety. Treatment assignments will be stratified by type of resection location. Patient randomization will be done via randomization program through REDCap. The randomization process will be performed centrally at Kansas University Medical Center and the treating surgeon will not have access to the randomization list. Randomization will occur prior to definitive surgical procedure, and the treating surgeon and pharmacy will be notified to ensure adequate vials of tranexamic acid are available in the operating room (investigators/surgeons are not blinded). Patients will be blinded to treatment allocation. Those in groups using TXA will receive 1g TXA IVPB 10 minutes prior to incision and a second dose of 1g IVPB at the time of closure which is the standard protocol used for total joint arthroplasty. The TXA will be administered by the anesthesia team. If the surgeon determines intraoperatively that TXA is required for patient safety, the drug should be used. Patients receiving a non-standard dosing of TXA will then be excluded from the study. Routine hemoglobin and hematocrit measurements will be observed preoperatively as well as postoperatively at 6 hours and in the mornings of postoperative days 1-3. This laboratory regimen is currently the standard of care and utilized routinely. Patients may be discharged prior to obtaining all 4 blood draws. If a patient is discharged prior to postoperative day 3, no additional blood draw will be performed. Additionally, both intraoperative and postoperative incidents of blood transfusion will be monitored to calculate transfusion rates. Postoperative erythrocyte transfusions will be given for hemoglobin below 7.0 as is the current practice guidelines used by the attending surgeons at this institution. Other facilities are encouraged to follow this protocol, however, the ultimate decision for blood transfusion will be at the discretion of the treating physician. Surgical drains are also used routinely and their daily output will be recorded until they are deemed appropriate to pull by the attending surgeon. Patients will be clinically monitored daily while in the hospital and in subsequent follow up visits for symptoms of DVT or embolism and appropriate diagnostic screening with venous Doppler will be utilized if symptoms are present, as is also part of current routine postoperative care. Our DVT prophylaxis protocol postoperatively will be 4 weeks of aspirin 81 mg BID unless medical co-morbidities necessitate the use of other anti-coagulation. Mechanical DVT prophylaxis in the form of sequential compression devices will also be

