
utilized. We also plan to record patient specific factors including age, sex, smoking status, BMI, pre-op diagnosis, operative time, comorbidities, and length of stay. These variables will be analyzed independently to detect any correlation with perioperative blood loss and erythrocyte transfusion rate.

C. Sample size, statistical methods, and power calculation

Method of Randomization: Patient randomization will be done via a randomization program through REDCap. The randomization process will be performed centrally at Kansas University Medical Center and the treating surgeon will not have access to the randomization list. Randomization will occur prior to definitive surgical procedure, and the treating surgeon and pharmacy will be notified to ensure adequate vials of tranexamic acid are available in the operating room (investigators/surgeons are not blinded). Patients will be blinded to treatment allocation. Treatment assignments will be stratified by type of resection. A power of 0.9 would require a total of 40 patients (20 per treatment group) be enrolled in the bony tumor group and 100 patients (50 per treatment group) in the soft tissue tumor group.

Since we are gathering entirely objective data the treating surgeon does not need to be blinded. Group differences in preoperative hemoglobin and hematocrit, transfusion requirements, drain output at 24 hours, and changes in hemoglobin and hematocrit will be compared using pairwise Student T-test analysis. Pairwise T-tests between each of the groups (for continuous variables) and Chi squared analysis (for categorical variables) will be used to determine if a statistically significant difference exists between the groups in terms of the patient specific factors that are also collected and analyzed (age, sex, smoking status, BMI, operative time, length of stay).

D. Subject Criteria (See Vulnerable Populations appendix, if applicable):

Inclusion criteria: Patients (male or female) between the ages of 18-90 undergoing wide resection of a malignant bony tumor of the lower extremity with endoprosthetic reconstruction or resection of soft tissue sarcoma measuring >5cm.

Exclusion criteria:

- Patients undergoing revision endoprosthetic reconstruction
- Patients with known coagulopathy
- Known history of DVT or embolic disease
- Benign tumors
- Patients with allergy to TXA
- Those refusing blood products
- Those concurrently on anti-coagulant therapy
- Pregnant and nursing women

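### The surgeon is told the arm before incision for a drug-supply purpose that does not require it; objective measurement does not prevent the resulting performance bias, and most hemostatic co-interventions are not listed for collection

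*Combined protocol and SAP*

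**What the plan says.** Section II.B (Study Type and Design), repeated in II.C (Sample size, statistical methods, and power calculation), sets the order of events:

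- "Randomization will occur prior to definitive surgical procedure".
- Then "the treating surgeon and pharmacy will be notified to ensure adequate vials of tranexamic acid are available in the operating room", with the remark that "investigators/surgeons are not blinded".
- The first dose in the TXA groups is "1g TXA IVPB 10 minutes prior to incision", and a second is given at closure. "The TXA will be administered by the anesthesia team".
- "Patients will be blinded to treatment allocation". No placebo or dummy infusion is described.

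Section II.C gives the reason for leaving the surgeon open: "Since we are gathering entirely objective data the treating surgeon does not need to be blinded".

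The primary outcome (II.A) is perioperative blood loss by the hemoglobin balance method. The analysis sections (II.C and V.A) also compare 24-hour drain output. Operative time is among the recorded factors and is compared between groups. V.A adds items such as resection size and depth, tumor location and stage. Tourniquet use, topical hemostatic agents, cell salvage and number of drains appear in neither list.

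**The concern.** The surgeon's technique helps determine how much the patient bleeds. A surgeon who knows before incision that no antifibrinolytic will be given can spend more effort on hemostasis, use a tourniquet, topical agents or cell salvage differently, or set up drains differently. A surgeon who expects TXA to work may behave differently in the other direction. The contrast then becomes TXA plus the surgeon's response to knowing it was given, against no TXA plus the surgeon's response to knowing it was not. An accurate hemoglobin value records that combined effect faithfully and cannot separate its parts. If the co-interventions are not collected, a reader of the results cannot judge whether they were balanced.

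**Working it through.** **1. Does the stated purpose need the surgeon?** The notice exists so that enough vials are in the operating room. Supply is pharmacy's task, and pharmacy is named in the same notice. Administration is anesthesia's task. The plan does not say how the anesthesia team learns the arm, so anesthesia should be added to the notice. Neither supply nor administration requires the surgeon to know.

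**2. Does the objectivity argument cover the risk?** Two biases should be kept apart:

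| Route | What it alters | Answered by objective data? |
|---|---|---|
| Measurement bias | The recorded value, given the true blood loss | Largely yes |
| Performance bias | The true blood loss itself | No |

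The sentence in II.C speaks to the first row. The surgeon's conduct of the operation belongs to the second.

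**3. What would be visible afterwards?** Operative time would show slower surgery, though not its cause, and TXA could itself shorten or lengthen a case. The other co-interventions are not listed variables.

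**4. How sensitive is the trial?** The documents give no standard deviation, target difference, alpha or sidedness, so the stated sample size cannot be reproduced. They give power 0.9 with 20 per arm (bone) and 50 per arm (soft tissue), 40 + 100 = 140 in all. Assuming two-sided 0.05, the standardized difference these numbers imply is

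d = (z₀.₉₇₅ + z₀.₉₀) × √(2/n), with 1.960 + 1.282 = 3.242:

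- bone: 3.242 × √(2/20) = 1.025 (noncentral t: 1.052)
- soft tissue: 3.242 × √(2/50) = 0.648 (noncentral t: 0.655)

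Now assume a performance bias of b standard deviations. This is my assumption; the documents do not supply b. With 2n − 2 degrees of freedom:

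- Bias favoring TXA and no true drug effect: noncentrality b × √(n/2). For b = 0.2 this is 0.2 × √10 = 0.632 (bone) and 0.2 × √25 = 1.000 (soft tissue).
- Bias against TXA and the implied d true: noncentrality (d − b) × √(n/2). For b = 0.2 this is 0.852 × 3.162 = 2.69 (bone) and 0.455 × 5 = 2.27 (soft tissue).

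| Assumed b (SD) | False-positive rate, bone | False-positive rate, soft tissue | Power, bone | Power, soft tissue |
|---|---|---|---|---|
| 0 | 5.0% | 5.0% | 90% | 90% |
| 0.1 | 6.1% | 7.9% | 83.5% | 78.4% |
| 0.2 | 9.5% | 16.8% | 74.7% | 61.5% |
| 0.3 | 15.2% | 31.8% | 63.9% | 42.0% |

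The false-positive columns take the bias as favoring TXA; the power columns take it as working against TXA. Enrolling more patients removes neither bias. The table shows sensitivity only and is no estimate of what will happen.

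**The case against.** The open surgeon is a declared choice with a stated reason, so it would be wrong to say that the plan gives none or overlooked the matter. That stands. What fails is the reason, which covers measurement and not conduct of the operation.

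The stronger objection is that concealment may achieve little. There is no dummy infusion, and the doses are tied to incision and closure, so a surgeon in the room may see whether a bag is hung. Section II.B also lets the surgeon call for TXA during the operation on safety grounds. A surgeon using that clause may well ask what has already been given, which reveals the arm in the bleeding cases that matter most. This stands as a limit on the remedy. Concealment will be partial and will often be lost in those cases. It is still an improvement on telling every surgeon every time, and it makes a record of who knew necessary.

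A reader might also infer that the bias could never be examined. The documents do not support that. Operative time is collected and compared between groups, and II.G draws endpoint data from electronic medical records, where some of these items may be found. The documents show only that the other co-interventions are not planned study variables.

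**Conclusion.** The point holds as a possibility created by the design. The surgeon learns the arm for a purpose that does not require it, the stated defense does not reach performance bias, and most of the relevant co-interventions are not listed for collection. All 140 planned patients are exposed. The remedy is a cheap and worthwhile improvement; the point does not invalidate the trial.

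Three stronger inferences are tempting and unsupported:

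- *That bias will occur, or in a known direction.* Extra effort in controls would hide a TXA effect, and a surgeon who favors TXA could exaggerate one. The documents do not say which.
- *That its size can be given in milliliters.* No standard deviation, target difference or co-intervention rate is stated. The figures in the working rest on an assumed b and two-sided 0.05.
- *That the surgeon's discretion over drain removal undermines the drain endpoint.* The analyzed variable is output at 24 hours, which removal affects only if it is very early. Drain number and set-up are the more relevant routes, and even there the effect is only possible.

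The transfusion decision is also open to influence by knowledge of the arm, but it is a separate matter and this conclusion does not rest on it.

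**What to change.** 1. **Notification (II.B and II.C).** Send the allocation to pharmacy and the anesthesia team, and not routinely to the treating surgeon. Leave the intraoperative safety clause as it is. Anesthesia tells the surgeon on request what has been given, and each disclosure is logged with its time. Amend the remark on surgeon blinding to match.
2. **Rationale (II.C).** Delete the sentence saying that objective data make surgeon blinding unnecessary, or limit it to measurement of the outcome and acknowledge that performance bias remains.
3. **Data.** Record tourniquet use and time, topical hemostatic agents, cell salvage, number of drains and, at the end of the case, whether the surgeon knew the arm.
4. **Analysis (V.A).** Tabulate these items and operative time by arm within the bone and soft-tissue strata. They arise after randomization and may respond to knowledge of the arm, so use them to describe and interpret the result, and not to exclude patients or adjust the primary comparison.

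The cost is a change in who receives the notice, about six short operative fields and a disclosure log. No placebo or extra staff is needed. The downside is partial concealment, often lost when a surgeon asks about TXA in a bleeding patient. If the sponsor keeps surgeons open, items 2 to 4 should still be done and the performance-bias limitation stated in the report.

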- Vulnerable populations as defined by the University of Kansas Medical Center IRB

Withdrawal/Termination criteria: The subject's participation will be terminated by the investigator if the subject wishes to withdrawal from the study at any point in time. In the event that a disproportionate number of complications are occurring in one of the study groups, the study will be suspended and the IRB will be consulted. There are no

safety precautions that need to be applied to subjects who withdraw from the study. The withdrawn patients will be routinely followed on an outpatient basis in a clinic setting.

E. Specific methods and techniques used throughout the study

1. Laboratory tests: Complete Blood Count (CBC) – the purpose of collection is to help determine the effect of TXA on hemoglobin and hematocrit levels. A CBC would be collected pre-operatively and post-operatively at 6 hours and in the mornings of postoperative days 1, 2, and 3. Patients may be discharged prior to obtaining all 4 blood draws. If a patient is discharged prior to postoperative day 3, no additional blood draw will be performed. Blood specimens will need to be collected for this test. This test is routinely ordered in the hospital setting and is the standard of care for evaluating and monitoring blood loss post-operatively.
2. Study Procedures: Describe each procedure to be used in the study, including the instruments used, time required for each procedure, cognitive assessments, etc. The patient's consented for this study and randomized to the TXA group will receive TXA while in the operating room as part of the routine administration of anesthesia. This is not technically considered a procedure.
3. Clearly indicate which procedures, tests, visits, etc., are parts of usual standard therapy and which are performed solely for research purposes. Make it clear which tests are routinely performed for clinical care but are providing data for the research (and are billable to insurance companies), and which tests are only performed for research purposes (not billable to insurance companies). Usual standard therapy: all postoperative clinic visits, pre-operative and post-operative CBC. These CBCs would be providing data for this clinical trial. No tests will be ordered that are only performed for research purposes.
4. Describe the fate of any body component: No body components will be obtained during this study.

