2. Primary responsibility for the following activities, for example:
 - a. Determining eligibility: [name] MD, [name] MD, [name], MD
 - b. Obtaining informed consent: [name] MD, [name] MD, [name] MD
 - c. Providing on-going information to the study sponsor and the IRB: [name] MD, [name] MD, [name]
 - d. Maintaining participant's research records: [name] MD, [name] MD, [name]
 - e. Completing physical examination: [name] MD, [name] MD, [name] MD
 - f. Taking vital signs, height, weight: Clinical support staff for participating surgeons
 - g. Drawing / collecting laboratory specimens: Clinical support staff for participating surgeons
 - h. Performing / conducting tests, procedures, interventions, questionnaires: [name] MD, [name] MD, [name] MD

- i. Completing study data forms: [name] MD, [name] MD, [name] MD, [name] MD
- j. Managing study database: [name] MD, [name] MD, [name]

L. Assessment of Subject Safety and Development of a Data and Safety Monitoring Plan

1. Please note that any study proposal with more than minimal risk must include a data and safety monitoring plan. Elements of the plan include:
 - a. Persons/groups who will review the data (study team; independent safety monitor, data monitoring committee or formal DSMB) - Study team
 - i. An independent safety monitor will be used. [name], MD is an orthopaedic surgeon familiar with the use of TXA and uninvolved with the study in any other capacity.
 - b. Data/events that will be reviewed - Adverse events/complications arising in the participating patients.
 - c. Frequency of review: Review will occur every 4 months routinely. Additionally, a review will be conducted if 5 separate adverse events are reported prior to the scheduled bi-annual review.
 - d. Types of analyses to be performed – we will analyze the rate of complications (infections, PE, DVT) between the groups to make sure that we aren't getting statistically significant differences between groups
 - e. Safety-related triggers that would cause the PI to stop or alter the study – If our analysis of complications reveals a statistically significant difference between groups, we will place the study on hold until an appropriate remedy can be reached. We will consult with the IRB before resuming the study. If no remedy can be determined the study will be permanently held

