1. Describe steps to be taken to assure that the data collected are accurate, consistent, complete and reliable. (source data verification, audits or self – assessment) Source data verification and self-audits will be performed. The protocol for the clinical trial will be spelled out for the participants. A discussion will be had between the PI at KUMC and the PI at the participating institution to ensure the protocol is understood.

V. Data Analysis and Reporting

A. Statistical and Data Analysis: Group differences in preoperative hemoglobin and hematocrit, transfusion requirements, drain output at 24 hours, difference in hemoglobin balance method, and changes in hemoglobin and hematocrit will be compared using pairwise Student T-test analysis. Pairwise T-tests between each of the groups (for continuous

variables) and Chi squared analysis (for categorical variables) will be used to determine if a statistically significant difference exists between the groups in terms of the patient specific factors that are also collected and analyzed (age, sex, smoking status, BMI, operative time, length of stay, presence of coagulopathy, specific anticoagulation regimen should it differ from study protocol, size of resection, depth of resection, location of tumor, pathologic diagnosis, stage of disease).

B. Outcome: We expect the results to be similar to the TXA arthroplasty studies/literature with regards to decreased perioperative blood loss and decreased transfusion rates. There are not necessarily any criteria for success or failure. The results of this study will help provide a definitive answer regarding the safety and efficacy of TXA in oncologic patients. This will help unify the musculoskeletal oncology field in their use or abandonment of TXA.

C. Study results to participants: The study results/conclusions will not be given to subjects unless they are specifically asked for at future scheduled outpatient clinic visits. Once the proposed study is completed a conversation with subjects can occur on an outpatient basis at their routine scheduled clinic visits regarding our results and conclusions if desired. The subjects reserve the right to know what conclusions were drawn from the study they directly participated in. In addition, we plan to publish a manuscript with our results/conclusions after completion of the study which can be sought after if desired.

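### Patients given off-protocol TXA are excluded after randomisation, and no as-randomised analysis is named to protect the primary comparison

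*Combined protocol and SAP*

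**What the plan says.** Section II.B sets out this sequence:

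- Assignment comes first: "Randomization will occur prior to definitive surgical procedure". The surgeon is told the assignment and is not blinded.
- The TXA groups "will receive 1g TXA IVPB 10 minutes prior to incision and a second dose of 1g IVPB at the time of closure".
- Off-assignment use is allowed: "If the surgeon determines intraoperatively that TXA is required for patient safety, the drug should be used". No bleeding criterion or other trigger is given.
- The next sentence removes the patient: "Patients receiving a non-standard dosing of TXA will then be excluded from the study". Non-standard dosing is not defined.

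The primary outcome (II.A) is perioperative blood loss by the hemoglobin balance method. Section V.A says that "difference in hemoglobin balance method, and changes in hemoglobin and hematocrit will be compared using pairwise Student T-test analysis". Neither II.C nor V.A names an intention-to-treat, as-randomised, per-protocol or as-treated set. The withdrawal text in II.D concerns patients who choose to leave. It keeps routine clinic follow-up for them but does not say whether their data are analysed. For safety, II.L says "we will analyze the rate of complications (infections, PE, DVT) between the groups", without saying whether excluded patients' events count. On sample size, II.C says: "A power of 0.9 would require a total of 40 patients (20 per treatment group) be enrolled in the bony tumor group". It gives 50 per arm for soft tissue and states no allowance for exclusions.

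**The concern.** A patient leaves the comparison because of something that happens during the operation whose blood loss is the primary outcome, on the decision of someone who knows the arm. TXA is given to reduce bleeding, so heavy bleeding is the plausible trigger. That is an inference, since the text states no trigger. If it is right, exclusion depends on the outcome.

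A heavily bleeding control seems more likely to receive off-protocol TXA than a patient already given the planned doses, so the likelier bias is toward no effect. The rule also covers TXA patients with missed or extra doses, and larger losses there would push the bias the other way. The retained patients cannot show which occurred.

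Safety is exposed too. The patients removed have off-protocol exposure to the study drug, and the between-group complication comparison that can put the study on hold may not count them.

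**Working it through.** **1. The plan's own figure.** The stated 0.90 power cannot be reproduced, because alpha, sidedness, effect size and SD are missing. Assuming two-sided 0.05, the implied standardised effect is d = (1.960 + 1.282) × √(2/n):

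- n = 20 per arm: 3.242 × 0.316 = 1.025 (1.052 with the t-test)
- n = 50 per arm: 3.242 × 0.200 = 0.648 (0.655 with the t-test)

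The t-test values are used below.

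**2. Whom the rule reaches.** The standard regimen starts before incision. A control first given TXA on an intraoperative decision cannot match that timing, and the word *then* ties exclusion to the preceding rescue sentence. On the natural reading, rescued controls are excluded. TXA patients with altered dosing fall under the same words.

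**3. Formula for the bias.** Let blood loss have SD 1, and let exclusion follow a score correlated ρ with blood loss. Removing the top share p of an arm lowers its mean by ρ × φ(z)/(1 − p), where z is the (1 − p) normal quantile. For p = 0.10, φ(1.282)/0.90 = 0.195. With ρ = 0.7 the shift is 0.7 × 0.195 = 0.137 SD.

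- Controls only: 1.052 − 0.137 = 0.92 (−13%); 0.655 − 0.137 = 0.52 (−21%).
- TXA arm only: 1.052 + 0.137 = 1.19 (+13%); 0.655 + 0.137 = 0.79 (+21%).

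**4. Simulation.** 40,000 trials per setting, normal outcome, pooled two-sided t-test, ρ = 0.7. Cells are bone / soft tissue.

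| Who is excluded | Effect (true 1.05 / 0.65) | Power | Error when there is no effect (nominal 2.5% each way) |
|---|---|---|---|
| 10% of controls only | 0.92 / 0.52 | 0.81 / 0.73 | false harm 6% / 10% |
| 10% of controls, 5% of TXA | 0.99 / 0.59 | about 0.87 / 0.82–0.85* | false harm 4% / 5–6%* |
| One bleeding threshold for both arms | 0.95 / 0.58 | 0.84 / 0.84 | 2.5% each way |
| 10% of each arm | unbiased | not reduced by bias | about 6% two-sided |
| 10% of TXA only | 1.19 / 0.79 | inflated | false benefit 6% / 10% |

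*5% of 50 is 2.5 patients; the range covers removing 2 or 3.

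Under the common threshold, 10% of controls but only 2.2% / 4.1% of TXA patients leave. Coverage of the 95% interval with control-only exclusion is 0.93 / 0.90.

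**5. Selection or smaller n?** Losing 10% at random from both arms gives no bias and power 0.86 in both strata. Losing 10% of controls at random leaves 0.88. The shifts in the table therefore come from selection.

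**6. Sensitivity.** Over 5–20% excluded and ρ from 0.5 to 1.0:

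- control-only power is 0.62–0.87 / 0.35–0.85
- common-threshold power is 0.73–0.88 / 0.69–0.88
- the TXA-only effect is 105–133% / 108–154% of the truth

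**7. As-randomised analysis.** With share p of controls rescued and rescue giving a fraction f of the TXA benefit, the estimate targets d(1 − f × p). At p = 0.10 and f = 1 this is 1.052 × 0.90 = 0.95 and 0.655 × 0.90 = 0.59. Under no effect the error is 2.5% each way. Power with full benefit from rescue is:

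- 5% rescued: 0.88–0.89 / 0.88
- 10% rescued: 0.85–0.87 / 0.85–0.86
- 20% rescued: 0.76–0.82 / 0.76–0.80

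**The case against.** The strongest reply has four parts.

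- **The mechanism and rate are assumed.** If rescue is rare (1 of 20, or 2 of 50), control-only exclusion still leaves power of about 0.85 in each stratum at ρ = 0.7. This stands: every magnitude above is illustrative.
- **The worst error rates need one-sided losses.** With one threshold for both arms, exclusion shrinks the effect by 9–11% and does not inflate the null error. This also stands, but nothing in the protocol imposes a common threshold, and the person applying the judgement knows the arm.
- **As-randomised analysis also attenuates.** At 10% rescue with full benefit it estimates 0.95 / 0.59, almost the same as common-threshold exclusion. Its interval covers the undiluted d in 0.93 / 0.93 of trials, and in 0.88 / 0.88 at 20% rescue. The study aims (II.A) speak of TXA used against not used, so the choice of target needs stating. This stands as a limit: the gain is validity, not power. Only the as-randomised comparison keeps the protection of randomisation whoever is rescued.
- **The outcomes are objective, so blinding is unnecessary (II.C).** This answers how blood loss is measured, not who stays in the comparison, and it does not meet the point.

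It is also fair to say that rescued controls are excluded on the natural reading. The missing definition matters more for late, missed or extra doses in the TXA arm, though no sentence settles how a control given the full two doses is classified.

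**Conclusion.** The concern holds and must be fixed: the rule is wrong as written. It removes patients from the primary comparison on an unblinded judgement made after randomisation, and no other section restores them.

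The size is unknown. With 10% of controls lost and ρ = 0.7, the effect is understated by 13% (bone) and 21% (soft tissue). Comparable losses in the TXA arm alone overstate it by the same amounts, and equal shares leave the mean unbiased. These figures assume normal outcomes, two-sided 0.05 and an effect set to give 0.90 power. The defect itself rests only on the text. With 20 per arm in bone, two exclusions are already 10% of an arm.

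**What to change.** In II.B, replace the exclusion sentence with:

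> All randomised patients who undergo the planned resection are analysed in the arm to which they were randomised; off-protocol TXA is recorded with time and reason, and outcome and adverse-event collection continues.

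The restriction to operated patients is there because the outcome cannot be measured without surgery; report by arm anyone randomised but not operated on.

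In V.A, name this set as the primary analysis and report off-protocol TXA by arm and stratum. Excluding these patients may remain as a labelled per-protocol sensitivity analysis, with non-standard dosing defined for it. In II.L, state that their complications count in the assigned arm.

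The cost is a few sentences. Blood counts, transfusions, drain output and visits are already routine care, and II.E says "No tests will be ordered that are only performed for research purposes", which remains true. The surgeon's discretion to give the drug is unchanged. The downside is dilution by crossover: at 20% of controls rescued with full benefit, power is about 0.79 (bone) and 0.78 (soft tissue), close to the 0.79 and 0.77 under common-threshold exclusion. If rescue on that scale is expected, the sample size should be reconsidered once its assumptions are stated.
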